## **6.13. Special Analytical Issues**

### **6.13.1. Treatment of incomplete or unmonitored data due to Covid-19 pandemic risk mitigation**

The Covid-19 pandemic during the final phase of this study may impact data collection in two different ways. Firstly, in order to avoid the risk of infection at the study sites, some of the subjects did not come to the site in person for the final study visit (V5); this visit was then

performed as a phone-call visit (virtual visit). And secondly, monitoring of some subject data was not possible due to unavailability of site staff.

Neither of these restrictions or changes has any impact on the primary study results, i.e., on analysis of the DTQ.

However the following data from V5 are expected to be missing for those subjects that completed V5 virtually: weight, HbA1c, pregnancy test, skin reaction assessment, device data upload, return of study material.

Missing data will be handled according to the description in section 3.4; no specific analysis pertaining to virtual visits will be performed.

The lack of monitoring however may result in wrong or missing entries in the eCRF. The monitoring status of all variables used for analyses will therefore be extracted from the eCRF and all variables, that have not been monitored, will be displayed underlined in all listings.

Additionally, all descriptive statistics and statistical tests based on data, that include data not monitored will be performed twice. Firstly, using the data as entered in the eCRF and secondly based on data generated by removing the data, that has not been monitored, and replacing it according to the missing value treatment described in section 3.4.

Differences in the statistics obtained using these two different approaches will illustrate the potential impact the data not monitored may have on study results.

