#### Subject Questionnaires

Subjects will be asked to complete a set of questionnaires at each visit, see section 7.10. These questionnaires will be presented electronically.

Upon completion of the questionnaires, the subject will press "Save" and close the document. This enables entries to be saved (in the eCRF). This will generate a notification to (named) study staff that the questionnaires have been completed/saved.

For the sake of confidentiality, neither the Investigator nor other study staff will be able to read the subject's entries.

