### 3.4. Handling of Withdrawals and other Missing Data

#### 3.4.1. Handling of missing data affecting the primary endpoint

As described in section 2.10, all randomized subjects will be part of the FAS group and thus be utilized for primary analysis. The status part (“Is this a problem now?”) of the DTQ will be completed by the subject before randomization. Thus it is ensured that status data is available for all subjects and that no bias is introduced by a potential preference of subjects for a particular group, which may result in a withdrawal of individual subjects right after randomization.

For subjects that answered the DTQ during Visit 4, these answers will be used for the primary analysis.

The following steps will be performed to handle missing change data:

In case of withdrawal, subjects will be asked to answer the DTQ questionnaire during the End of Study visit.

If it will not be possible to get questionnaire results at the End of Study visit but questionnaire results are available for week 13 (visit 3), these results will be used, i.e., a LOCF procedure will be applied.

If there are no results for week 13, e.g., because a subject withdrew before week 13, a value of 3 (“Same”) will be imputed as the answer to every individual question. This will result in a total score of 90, which corresponds to the expected mean result for the MDI group and thus represents a conservative imputation (the anticipated mean score for the Accu-Chek® Solo group is 110).

Technically, data acquired during the End of Study visit will be part of the Visit 5 eCRF variables. Consequently, the LOCF procedures described above will copy data from there. Should the End of Study data be not available, the respective data of the available last visit will be used.

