### **3.4.3. Handling of empty fields in the diabetes medication forms**

Investigators are only supposed to enter insulin doses if they differ from 0. Consequently, empty fields in the insulin dose fields are considered normal and will simply be imputed with 0 for analysis. Insulin to carbohydrate ratios will be handled similarly. Investigators usually only enter data if they differ from those entered previously. In order to account for this fact, empty values in these forms will be imputed with the value from the previous timepoint. This applies for the variables “Units”, “Grams”, and “mg/dl” respectively “mmol/l” in the diabetes medication forms.

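### The SAP's second run on unmonitored data fills deleted insulin doses with 0 and deleted Visit 5 values with Visit 4 values, so its gap from the as-entered run mixes imputation with data quality

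*SAP*

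**What the plan says.** SAP 6.13.1 deals with data that monitors could not check during the pandemic. It states that "all descriptive statistics and statistical tests based on data, that include data not monitored will be performed twice". The first run is described as "Firstly, using the data as entered in the eCRF". The second is made by "removing the data, that has not been monitored, and replacing it according to the missing value treatment described in section 3.4". The purpose is given as: "Differences in the statistics obtained using these two different approaches will illustrate the potential impact the data not monitored may have on study results". The same section says that neither virtual visits nor missing monitoring "has any impact on the primary study results".

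SAP section 3.4 has different rules for different data:

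- **eCRF insulin doses (3.4.3).** An empty dose field "will simply be imputed with 0 for analysis". The reason given is that investigators enter a dose only when it is not zero.
- **Other entries in the diabetes medication forms (3.4.3).** These take the value from the preceding timepoint. The list of variables includes the units field.
- **DTQ (3.4.1).** Visit 4 answers are used if present, then End of Study answers (held in the Visit 5 variables), then Visit 3. Only after that is a value of 3 used, which "will be imputed as the answer to every individual question".
- **Other scores (3.4.4).** Last observation carried forward, where that applies.
- **Device data (3.4.4).** Glucose readings and pump insulin amounts are analysed as available, without imputation.

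Under the Subject Questionnaires heading in section 7.13, the Protocol says of the subjects' entries that "neither the Investigator nor other study staff will be able to read" them.

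**The concern.** The gap between two runs shows the effect of questionable entries only if the values put in their place are neutral. Two of the section 3.4 rules are not.

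The zero rule translates a blank into what the investigator meant by it. A deleted dose is the opposite case: a dose was entered, and it was not zero.

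Carrying Visit 4 forward sets a subject's Visit 4 to Visit 5 change to zero. In arms B and C, Visit 4 is the last assessment on MDI or OmniPod, so a value from the previous treatment is counted in the Solo phase.

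Both affect planned output. SAP 6.8.2 tabulates eCRF basal and bolus doses and their differences between visits, 6.8.5 tabulates changes from pre-study doses, and 6.8 plans within-arm comparisons of Visit 4 with Visit 5. Device uploads exist only for pump users (6.8.5), so in the MDI arm the eCRF is the only source of dose. A reader following 6.13.1 could see a data-quality problem where there is none, or miss a real one that the imputation offsets.

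**Working it through.** **Inputs.** The replacement rules are those of SAP 3.4. The DTQ planning values (means 90 and 110, SD 30, 49 evaluable and 60 enrolled per arm, 18% drop-out) are from SAP 2.8. The documents do not give the unmonitored share f, so 5%, 10%, 20% and 30% are assumed, equal across arms and unrelated to the values themselves. A mean eCRF dose of 40 U/day with SD 16 is assumed for illustration only; the proportional result does not depend on it.

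**1. The plan's own figures.** 30 × 3 = 90, as stated. For a difference of 20 and SD 30, the exact t calculation gives power 0.904 at 49 per group and 0.898 at 48. 49 / (1 − 0.18) = 59.8, so 60. These reproduce and are not in dispute.

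**2. What the gap contains.** Let the deleted entries have true mean μ, let them carry an average entry error b, and let the replacement have mean r. The as-entered mean minus the second-run mean is

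f × (μ + b − r).

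It equals f × b, the quantity of interest, only if r = μ. With r = 0 for doses, the gap is f × (μ + b). For a Visit 4 to Visit 5 change with true mean D, where the replacement gives a change of 0, it is f × (D + b).

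**3. Size when every entry is correct (b = 0).**

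- Dose mean: (1 − f) × 40. Dose variance: (1 − f) × 16² + f(1 − f) × 40².
- Mean Visit 4 to Visit 5 change: (1 − f) × D.

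| f | Mean dose, U/day (as entered 40) | SD (as entered 16) | Share of V4–V5 change kept |
|---|---|---|---|
| 5% | 38 | 17.9 | 95% |
| 10% | 36 | 19.3 | 90% |
| 20% | 32 | 21.5 | 80% |
| 30% | 28 | 22.7 | 70% |

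If only the Visit 5 dose is deleted and the Visit 4 dose is kept, the dose change does not shrink. It gains a spurious fall of f × 40 = 2, 4, 8 or 12 U/day. If f differs between arms, an arm difference appears: 10% in one arm and 20% in another give 36 against 32 U/day from identical true doses.

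**4. The DTQ as an outer bound.** A subject reaches 90 only if the Visit 3, Visit 4 and Visit 5 questionnaires are all removed or missing. If a share f of both arms were in that state, the planned difference would be 20 × (1 − f) = 19, 18, 16 and 14. Taking the average of the two arm variances, (1 − f) × 900 + f(1 − f) × 400 for Solo and (1 − f) × 900 for MDI, power at 60 per arm would be 0.939, 0.925, 0.887 and 0.835. Nothing in the documents suggests that this state would arise.

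**The case against.** **The zero rule may not apply to deleted doses.** SAP 6.8.2 builds the dose tables from the last recorded change before each visit, medication after Visit 1 is recorded only when it changes, and 3.4.3 itself lists the units field among those taking the previous value. A deleted change record might therefore fall back to the record before it. This makes the outcome ambiguous, but 6.13.1 points to section 3.4, where the rule for empty dose fields is zero. The other reading is not neutral either: a Visit 5 dose would revert to an earlier one, which in arms B and C can be the dose before the switch.

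**Reach is limited.** The as-entered run is kept, unmonitored values are underlined in the listings, and no decision rule hangs on the second run. Device uploads are not imputed. Carrying Visit 4 forward needs a retained Visit 4 value. Neither the primary endpoint nor the HbA1c test in 6.8.1.2 (Visit 4 minus Visit 2) uses the Visit 4 to Visit 5 change. All of this stands.

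**The DTQ.** A reader might infer that the second run turns DTQ answers into 90. The documents do not support that. The value 90 is the last of four steps, 6.13.1 says the DTQ analysis is unaffected, and nothing shows that subject-entered questionnaires count as unmonitored. What remains is a missing sentence: 6.13.1 extracts monitoring status for every analysed variable and exempts none. If a Visit 4 DTQ were flagged, it is unclear whether 3.4.1, written for withdrawals, would bring in Visit 5 answers that arms B and C gave on Solo.

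**Conclusion.** The point holds for eCRF insulin doses and for Visit 5 values filled from Visit 4. For these, the second run differs from the first by a fraction f of the mean dose or mean change even if no entry is wrong: 5% to 30% over the assumed range. This assumes that unmonitored subjects resemble the others on average, that 3.4.3 is applied to deleted doses as written, and that Visit 4 is retained. For weight and HbA1c it also assumes that carrying forward extends to them; 6.13.1 sends missing Visit 5 values of both to section 3.4, which offers no other rule.

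A reader might go further and say that the second run measures only the imputation. That is too strong: by step 2 an entry error still contributes f × b, but it cannot be separated from the imputation term. The weakness lies in a secondary sensitivity comparison; the primary conclusion is not shown to be affected. It is worth correcting because the SAP attaches a specific interpretation to the gap and the repair is simple.

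**What to change.** Amend SAP 6.13.1 as follows.

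1. Run the second analysis on monitored data only, without section 3.4 imputation of the removed values. At minimum, do not apply the zero rule to deleted dose fields or carry Visit 4 into Visit 5 for removed values. In the notation above, the gap then becomes f × (μ + b − mean of the monitored values), which is f × b when the two sets of subjects are alike.
2. State that subject-entered electronic questionnaires, including the DTQ, are not removed, in line with the section's own statement on the DTQ. Central-laboratory HbA1c should not be exempted on the same ground: the documents do not show that it reaches the eCRF without a site entry step, and Protocol 13.4.1 has monitors check eCRF entries against laboratory reports.
3. Reconcile 3.4.3 with 6.8.2 on what an empty units field means.
4. Report the number of removed values by arm and visit, so that f is visible.

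The cost is SAP wording, fewer observations and wider intervals in the second run. A monitored-only run can still differ from the first if unmonitored subjects differ from the rest, and the report should say so.

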### **6.13.2. Examination of Subgroups**

The analysis of all variables will be repeated for all defined subject populations. No explicit additional subgroup analysis will be performed. Different results in the various populations will not be compared explicitly but only mentioned in the report where appropriate.

### **6.14. Quality assurance**

All statistical programs employed in the analysis and reporting of the data will be validated according to the standard operating procedures (SOP 04.04.50 V1) and results will be checked for plausibility.
